9.4 TREATMENT DOSE MODIFICATIONS AND TREATMENT CYCLE DELAY

9.4.1 NOX66

Any patient who experiences toxicity > Grade 2 related to NOX66 will have the idronoxil treatment withheld for 1 day and then resume on the next lower dosage (1200 mg reduced to 800 mg; 800 mg reduced to 400 mg; 400 mg daily reduced to 400 mg every 2nd day) for the remainder of the treatment period.

If toxicity > Grade 2 persists following reduction of dose, the idronoxil treatment will cease immediately for the remainder of the treatment period, although the patient may remain in the study.

There will be no dose modification of NOX66 on the basis of body weight.

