3.4 MEDICAL OVERSIGHT

Medical management and patient care while participating in this study is the responsibility of the Principal Investigator. Review of adverse events and decisions on continuation in trial, medical intervention and other related activities for an individual patient shall be at the discretion of the Principal Investigator. Review of adverse events and decisions on continuation in trial, medical intervention and other related activities for the overall study shall be at the discretion of the Study Steering Committee – consisting of Principal Investigators, an independent Oncologist and a representative of the Sponsor company.

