8.4 SCREEN FAILURE AND STUDY WITHDRAWAL

Patients should begin protocol treatment within 2 weeks of enrolment at screening. Issues that would cause treatment delays longer than 2 weeks should be discussed with the Sponsor. If a patient does not proceed to receive protocol therapy following enrolment at screening, the patient's study enrolment will be cancelled, and the patient will be considered a screen failure. The Sponsor should be notified of screen failures as soon as possible.

Patients will be informed that they are free to withdraw from the study at any time and for any reason. Withdrawal criteria, other than progressive disease, can be defined as one or more of the following:

- an inter-concurrent illness that prevents further administration of idronoxil (NOX66) or radiation therapy;
- an adverse event to the combination treatment that is intolerable;
- the patient withdraws consent;
- the patient dies;
- general or specific changes in the patient's condition render the patient unacceptable for further treatment in the judgment of the Investigator.

In all cases, the reason for withdrawal must be recorded in the CRF and in the patient's medical records. The patient must be followed to establish whether the reason was an adverse event causally related to idronoxil (NOX66), and, if so, this must be reported in accordance with the requirements for adverse event reporting.

Patients will continue to be followed for the duration of the study, unless consent is withdrawn.

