Patient may be contacted by telephone after enrolment as a reminder to start NOX66 administration day prior to attending clinic for radiation therapy.

10.2.3 Treatment Cycle (Days 1-16) - Visits 2 to 7

Treatment will Commence on Day 1 of the Study Visit Schedule (Table 1) and the procedures for Treatment Visits are listed below in Table 1.

Overall, the patient will attend the clinic on 7 days during the Treatment Cycle.

During the Treatment Cycle, the patient will receive treatment of:

- NOX66 (Dose dependent on treatment cohort) for 13 up to 16 consecutive days (Days 1-16), inclusive of weekends and public holidays.
- Palliative radiation therapy (20Gy Dose) in five fractions over 8 days commencing on Day 2 to Day 9. Radiation therapy **not given** on weekends and public holidays.

Table 1. Schedule of Assessments: TREATMENT CYCLE

Period	Pre-RT		RT									Post RT					EoT ³
	D0 (-7)	D 1	D 2	D 3	D 4	D 5	D 6	D 7	D 8	D 9	D 10	D 11	D 12	D 13	D 14	D 15	D 16+1
VISITS	V1 ¹		V2	V3 - V6 ²													V7
NOX66 (Self-administration)		X	X	X	X	X	X	X	X	X	X	X	X	X	X	X	X ⁴
Radiation therapy			X	X													
Physical exam			X														X
ECG																	X
Vital Signs			X														X
Complete Blood Count																	X
Serum chemistry																	X
Urinalysis																	X
Biomarker ⁵	X																X
BPI-SF ⁶ Questionnaire																	X
Concomitant medications/ Adverse Event ⁷ review			X	X													X
Dispense NOX66	X																
Return NOX66																	X

¹Enrolment-Visit to occur after eligibility confirmation (Screening) and prior to V2, to receive NOX66 and education on self-administration

² Patient attend clinic for 5 days in an 8-day period to receive RT. Patient will not attend clinic on days where RT is not conducted

³ End of Treatment (EoT) visit to occur Day following last dose of NOX66

⁴NOX66 dosing continues to Day 16 if there has been (weekend and public holiday -up to 3 days) interruption in RT in Treatment Cycle.

⁵ Biomarkers include idronoxil

⁶ Brief Pain Inventory-Short Form (1991)

⁷ Adverse Event (AE) assessed by Investigator using the NCI CTCAE v4.03 scoring system

10.2.4 Six-Week Follow up (Day 43 ± 5) - Visit 8

Visit 8 will occur 28 days/4 weeks post completion of NOX66 treatment and consist of the following assessments:

- Physical Examination including vital signs
- Performance Status Assessment (using ECOG performance scale)

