13.2 SAFETY DATA MONITORING

The Study Steering Committee (SSC) will review and evaluate all toxicities causally associated with NOX66 treatment and or the radiation therapy combination therapy. The SSC will consist of:

- Principal Investigator from each clinical site, or medical designee
- Sponsor's Medical Monitor
- CRO Medical Representative (if applicable)
- Director of Clinical Development, Noxopharm Ltd

Review of any adverse events of Grade 2 toxicity and above, considered by the Principal Investigator to be related to idronoxil (NOX66), will be reported to the SSC immediately and decision on the continuation of the patient individually, and the study in general, will be provided.

The Study Steering Committee will review the Safety Data and determine dose cohort escalation following completion of treatment cycle (Visit 7) of final patient in a cohort.

The SSC will determine the dose for cohort expansion based on the review of accumulated safety data, on treatment response and disease evaluation following WEEK 6 assessments of all patients and determine continuation of the study.

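### Section 9.4.1 restarts NOX66 after a fixed one-day hold for related toxicity above Grade 2 without requiring recovery, and no adverse event review is scheduled in the last 7 dosing days

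*Combined protocol and SAP*

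**What the plan says.** Under section 9.4.1, toxicity above Grade 2 that is related to NOX66 leads to one course of action: the patient "will have the idronoxil treatment withheld for 1 day and then resume on the next lower dosage". The steps are 1200 to 800 mg, 800 to 400 mg, and 400 mg daily to 400 mg every second day. If toxicity above Grade 2 "persists following reduction of dose, the idronoxil treatment will cease immediately for the remainder of the treatment period".

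Other sections bear on the same patient:

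- Section 3.4 places review of adverse events and decisions on continuation "for an individual patient shall be at the discretion of the Principal Investigator", and decisions for the study as a whole with the Study Steering Committee (SSC).
- Section 8.4 lists as withdrawal criteria "an adverse event to the combination treatment that is intolerable" and changes in condition that "render the patient unacceptable for further treatment in the judgment of the Investigator".
- Section 13.2 sends related events of Grade 2 and above to the SSC at once and says that a "decision on the continuation of the patient individually, and the study in general, will be provided". SSC members include the "Principal Investigator from each clinical site, or medical designee".
- Table 1 (section 10.2.3) schedules adverse event review on the five radiation days and at the end-of-treatment (EoT) visit, which falls the day after the last dose. Its footnote 2 adds: "Patient will not attend clinic on days where RT is not conducted".
- Section 9.2 continues NOX66, self-administered, for 7 days after radiation ends.

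**The concern.** Read literally, 9.4.1 re-doses after one day a patient whose related Grade 3 or higher toxicity may still be present. The length of the hold is fixed, and nothing in the section makes resumption depend on the patient's state. The built-in stop cannot prevent that re-exposure, because it tests for persistence only at the reduced dose.

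The stop also depends on someone seeing that the toxicity has persisted. A patient who restarts around the last fraction takes the rest of the course at home with no planned review until dosing is over. Safety and tolerability are the primary objective, so the rule for managing the most serious related toxicities should be sound when it is needed.

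**Working it through.** The plan gives no event rate for this rule, so the check is a reading of the text plus a count of days.

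**1. Length of dosing.** Inputs: one day before radiation and 7 days after it (9.2); five fractions over five to eight days (9.3, Table 1).
- Shortest: 1 + 5 + 7 = 13 days (radiation on Days 2 to 6).
- Longest: 1 + 8 + 7 = 16 days (radiation on Days 2 to 9).

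This reproduces the 13 to 16 days in the synopsis and section 10.2.3.

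**2. Scheduled adverse event reviews on dosing days.** These are visits V2 to V6, five in all.
- 5/13 = 38%; 5/16 = 31%.
- V7 (EoT) does not count, because it comes the day after the last dose.

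**3. Dosing days after the last fraction.** Days 7 to 13 or Days 10 to 16, so 7 in either case.
- 7/13 = 54%; 7/16 = 44%.
- Scheduled reviews in those days: 0.

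**4. Example: toxicity first seen at the last fraction.** Assume that the hold falls on the next day.
- Fraction 5 on Day 6: hold Day 7, resume Day 8, last dose Day 13, EoT Day 14.
- Fraction 5 on Day 9: hold Day 10, resume Day 11, last dose Day 16, EoT Day 17.

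Either way the remaining course is 6 days (8 to 13, or 11 to 16), and the next scheduled review comes after all of them. For a patient reduced to alternate days, 3 of those 6 are dosing days.

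**5. Does another section supply what 9.4.1 lacks?**

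| Section | Stop route or follow-up duty | Recovery condition before restart | Longer hold | Fixed contact in the last 7 dosing days |
|---|---|---|---|---|
| 3.4 | Yes, investigator | No | Not stated | No |
| 8.4 | Yes, withdrawal | No | No | No |
| 13.2 | Yes, a decision after report to the SSC | No | Not stated, no deadline | No |
| 14, 14.2.1 | Follow-up of known events | No | No | No |
| 9.6, 18.1.1 | Monitoring and availability in general terms | No | No | No |

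Section 15.3 permits deviations only in emergencies, and section 9.5 forbids use of NOX66 except as the protocol directs. An investigator who wants two or three days for recovery before restarting therefore has no stated route. By contrast, inclusion criterion 11 requires toxicity from prior therapy to have settled to Grade 1 or less before the first dose.

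**6. Cost of a longer hold.** Each extra day is 1/16 to 1/13 of the dosing days, or 6% to 8%.

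**The case against.** The best defence is that 9.4.1 does not stand alone. Every event that triggers it also meets the lower threshold in 13.2, so it goes to the SSC immediately. The investigator grades the event (Table 1, footnote 7) and may stop treatment under 3.4 or 8.4. Serious events reach the Medical Monitor within 24 hours (14.2), and known events must be followed (14, 14.2.1). A short hold also has a rationale: section 4.5 reports that in rats the drug is largely cleared within a day, and section 5.2 wants drug present while damage is induced and repaired. Finally, section 5.3 reports no Grade 2 or higher events with the intravenous and oral forms.

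Much of this stands. It rules out three stronger readings that a reader might infer:

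- **That the protocol has no decision step for such a patient.** This is true of 9.4.1 read alone; 3.4, 8.4 and 13.2 supply routes.
- **That 3.4 and 13.2 contradict each other on who decides.** The sentence in 13.2 is passive and names no decider. The SSC is the natural reading but not the only one, and investigators sit on the SSC. A cross-reference is enough.
- **That the rule distorts dose escalation.** Section 10.2.14 counts discontinuations due to NOX66-related events, so whether one patient stops or resumes can matter. But the SSC reviews the safety data before escalating, and the documents give no rate from which to compute an effect.

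The defence does not reach the core. Clearance of drug in rats does not show that a toxicity has resolved in a patient. The routes in other sections allow a stop but set no condition for restarting. A duty to follow an event is not a contact on a given day. The history in 5.3 is from other formulations. Section 4.5 puts metabolism of the oral form above 99% and says that NOX66 was made to reduce it, so that record may not carry over.

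**Conclusion.** The point holds as a moderate flaw in a safety rule that should be fixed. As written, 9.4.1 can re-dose a patient with ongoing Grade 3 or higher related toxicity after one day, and its stop acts only after re-exposure. For a patient who restarts around the last fraction, persistence may go unchecked until the course is finished. The measurable part is 7 of 13 to 16 dosing days without a scheduled review. These are proportions of days, not of harm.

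The conclusion assumes that sites follow 9.4.1 as worded and that the schedule in Table 1 is the only planned contact. The frequency of related toxicity above Grade 2 with NOX66 plus radiation is not in the documents, so the rule may be used rarely.

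**What to change.** **Section 9.4.1.** Withhold NOX66 for at least 1 day. Resume at the next lower dosage only once the Principal Investigator documents that the toxicity has fallen to Grade 2 or below. That is the rule's own threshold; the sponsor may prefer Grade 1, in line with inclusion criterion 11. If this is not reached before the planned end of the treatment period, do not resume, and record the patient as discontinued due to a NOX66-related adverse event. Keep the existing stop for persistence after reduction.

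**Contact.** For any patient who resumes at or after the last fraction, add one telephone call before the EoT visit to ask whether the toxicity has persisted.

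**Clarification.** Cross-refer 9.4.1 to 3.4 and 13.2, leaving SSC review of individual cases in place.

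**Cost.** Amended wording, a CRF entry for the grade and date at resumption, and a call for the few patients concerned. No routine clinic visit and no extra patients are needed. A laboratory toxicity would need a repeat sample, because Table 1 schedules blood tests in the treatment cycle only at EoT. Patients may miss a few doses, each day being 1 of 13 to 16. Some may stop who would have resumed, and anyone dosed for fewer than 7 days leaves the efficacy population (12.2). That is an acceptable price in a study whose primary objective is safety.

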9.4.2 Radiation Therapy

There will be no dose modification of radiation therapy. Any deviation from the planned dose of radiation therapy will be reported by the investigator in the CRF.

9.5 ACCOUNTABILITY FOR CLINICAL SUPPLIES

The Principal Investigator or delegate/s will be responsible for the dispensing, inventory, and accountability of all clinical supplies, exercising accepted medical and pharmaceutical practices. An accurate and timely accountability record log of the disposition of all clinical supplies must be maintained. The supplies and inventory record must be made available for inspection by the Sponsor or the designated Sponsor's representative upon request. All used medication packaging and unused medication will be collected and retained until completion or termination of the study. Once all drug accountability has been performed and monitored the Investigator or delegate/s will destroy NOX66 as per Site Pharmacy SOPs and/or return all remaining clinical supplies to the Sponsor who will destroy the study drug on the site's behalf. Under no circumstances will the Principal Investigator allow NOX66 to be used other than as directed by this protocol.

9.6 CONCOMITANT MEDICATIONS

Patients are permitted a wide range of medications for general health, although this is to be confirmed with the Sponsor prior to enrolment into the Study.

Patients are permitted certain medications specifically related to their metastatic disease, including use of androgen deprivation therapy (ADT) such as luteinizing hormone-releasing hormone (LHRH) agonists and antagonists. Other therapies are to be confirmed with the Sponsor medical monitor prior to enrolment in the Study.

Patients are not permitted any other experimental treatments. Supportive care measures and treatment for symptom control are permitted, including analgesics. Treatment of constipation or diarrhea is permitted however the investigator must determine the suitability of these patients to continue taking suppositories should these adverse events (as scored by NCI CTCAEv4.03) be reported. Patients will be medically monitored so that any adverse events will be identified promptly and treated appropriately.

Details regarding the name, indication, route of administration, dose, and frequency of all medications taken within 14 days prior to study drug administration will be recorded in the eCRF at the Screening Visit and Day 1. Details regarding the name, indication, route of administration, dose, and frequency of all medications taken during the study will be recorded in the eCRF at each patient visit. "All medications" should include prescription, over-the-counter (OTC) medications, dietary/nutritional supplements, and herbal products.

10 STUDY PROCEDURES

10.1 OUTCOME MEASURES

The outcome measures supporting the primary objective of this study are:

- Number of events of > Grade 2 toxicity (as scored by CTCv4.03)
- Number of events of > Grade 2 toxicity considered by the investigator and / or the Sponsor as causally related to the use of NOX66 (as scored by CTCv4.03)
- The overall number of adverse events considered by the investigator and / or the Sponsor as causally related to the use of NOX66
- Incidence of dose limiting toxicities (DLT) and or maximum tolerated dose (MTD) of NOX66

The outcome measures supporting the secondary objectives of this study are:

- Where target (measurable) lesions have been identified:
 - a. Change intumour size of irradiated lesions according to RECIST1.1 criteria, as assessed by central review and by the investigator based on CT/MRI scan
 - b. Change in tumour size of target non-irradiated lesions according to RECIST1.1 criteria, as assessed by central review and by the investigator based on CT/MRI scan
 - c. Observation of change from baseline in Non-target lesions according to RECIST 1.1 criteria
- For all patients – overall assessment of change in disease state by an independent Radiation Oncology Expert Committee
- Change from baseline in pain score based on responses to BPI-SF
- Observation of change from baseline in PSA levels
- Assessment of patient via physical exam and ECOG Score

- Plasma level of idronoxil post treatment (immediate and long term (at 6 weeks))
- Duration of tumour progression free state from study treatment start date
- Duration of survival from study treatment start date

10.2 STUDY VISITS

The total study duration per patient will be a minimum of 25 weeks, with continued follow up up to 24 months from the treatment commencement date:

- Screening period: to occur within 2 weeks prior to the scheduled date of treatment commencing
- Treatment and follow up period: up to 24 weeks from the commencement of the first dose of NOX66 and it includes enrolment visit to occur prior to Day 1 of treatment
Long term follow up visits: every 3 months from week 24 for another 18 months.
Observation period (post study follow-up visits): Continued observation of patients beyond 24 months follow up visit, at the discretion of the investigator.

10.2.1 Screening Visit (VS)

The purpose and the procedures of the Study will be fully explained to participants at the screening visit and every patient approached regarding the study will be provided with the Informed Consent Form (ICF). Patients wishing to enrol in the Study will sign the ICF prior to initiating any study related investigations or procedures.

All screened patients who sign the ICF must be recorded on the Screening/Enrolment Log. If a patient who signs an ICF is not enrolled in the study, the reason will be noted. The Screening/Enrolment Log will be retained within the Investigator Site File.

The following procedures are to be performed at the screening visit to occur within 2 weeks of commencement of NOX66 treatment:

- Obtain Informed Consent
- Review and confirm eligibility (Inclusion / Exclusion Criteria)
- Medical History and Demography, including review of any prior radiation therapy and toxicities / adverse events
- Physical Examination including vital signs
- Performance Status Assessment (using ECOG performance scale)
- Safety blood sampling – Complete Blood Count, Serum Chemistry, and Urinalysis; and results within 5 days of enrolment
- Blood sample for serum PSA and testosterone
- Electrocardiography (12-lead) in triplicate
- Concomitant Medication Review
- Tumour Imaging (CT/MRI) including measures of target lesions- baseline
- Administration of Brief Pain Inventory -Short Form questionnaire

Radiological scans performed prior to consent may be utilized for the purposes of the study if they have been performed as part of routine clinical practice and the patient consents for their medical records to be reviewed by the Sponsor, the scans were performed in the 28 days prior to the screening visit (i.e. they can be considered current evidence of tumour size) and they can provide suitable tumour measurements and assessments of target and non-target lesions.

The Principal Investigator will maintain a confidential log of all patients who have been screened for participation in the study whether or not the patient was eligible for study participation

10.2.2 Enrolment Visit (V1):

Once eligibility is confirmed patients will be contacted to attend clinic for:

- education on self-administration and dispensing of NOX66 for use from Day 1 of the treatment cycle
- baseline biomarker blood sample for idronoxil

Patient may be contacted by telephone after enrolment as a reminder to start NOX66 administration day prior to attending clinic for radiation therapy.

10.2.3 Treatment Cycle (Days 1-16) - Visits 2 to 7

Treatment will Commence on Day 1 of the Study Visit Schedule (Table 1) and the procedures for Treatment Visits are listed below in Table 1.

Overall, the patient will attend the clinic on 7 days during the Treatment Cycle.

During the Treatment Cycle, the patient will receive treatment of:

- NOX66 (Dose dependent on treatment cohort) for 13 up to 16 consecutive days (Days 1-16), inclusive of weekends and public holidays.
- Palliative radiation therapy (20Gy Dose) in five fractions over 8 days commencing on Day 2 to Day 9. Radiation therapy **not given** on weekends and public holidays.

Table 1. Schedule of Assessments: TREATMENT CYCLE

Period	Pre-RT		RT									Post RT					EoT ³
	D0 (-7)	D 1	D 2	D 3	D 4	D 5	D 6	D 7	D 8	D 9	D 10	D 11	D 12	D 13	D 14	D 15	D 16+1
VISITS	V1 ¹		V2	V3 - V6 ²													V7
NOX66 (Self-administration)		X	X	X	X	X	X	X	X	X	X	X	X	X	X	X	X ⁴
Radiation therapy			X	X													
Physical exam			X														X
ECG																	X
Vital Signs			X														X
Complete Blood Count																	X
Serum chemistry																	X
Urinalysis																	X
Biomarker ⁵	X																X
BPI-SF ⁶ Questionnaire																	X
Concomitant medications/ Adverse Event ⁷ review			X	X													X
Dispense NOX66	X																
Return NOX66																	X

¹Enrolment-Visit to occur after eligibility confirmation (Screening) and prior to V2, to receive NOX66 and education on self-administration

² Patient attend clinic for 5 days in an 8-day period to receive RT. Patient will not attend clinic on days where RT is not conducted

³ End of Treatment (EoT) visit to occur Day following last dose of NOX66

⁴NOX66 dosing continues to Day 16 if there has been (weekend and public holiday -up to 3 days) interruption in RT in Treatment Cycle.

⁵ Biomarkers include idronoxil

⁶ Brief Pain Inventory-Short Form (1991)

⁷ Adverse Event (AE) assessed by Investigator using the NCI CTCAE v4.03 scoring system

10.2.4 Six-Week Follow up (Day 43 ± 5) - Visit 8

Visit 8 will occur 28 days/4 weeks post completion of NOX66 treatment and consist of the following assessments:

- Physical Examination including vital signs
- Performance Status Assessment (using ECOG performance scale)
- Safety blood sampling – Complete Blood Count, Serum Chemistry and Urinalysis
- Biomarker blood sampling – PSA and idronoxil
- Administration of Brief Pain Inventory -Short Form questionnaire
- Concomitant Medication Review
- Adverse Event Review (CTCAE 4.03)
- Tumour Imaging (CT/MRI scan) and Assessment

10.2.5 Twelve-Week Follow up (Day 84 ± 7) - Visit 9

Visit 9 will occur 70 days/10 weeks post completion of NOX66 treatment and consist of the following assessments:

- Physical Examination including vital signs
- Performance Status Assessment (using ECOG performance scale)
- Electrocardiography in triplicate
- Safety blood sampling - Complete Blood Count, Serum Chemistry and Urinalysis
- Biomarker blood sampling – PSA
- Administration of Brief Pain Inventory -Short Form questionnaire¹
- Concomitant Medication Review
- Adverse Event Review (CTCAE 4.03)
- Tumour Imaging (CT/MRI scan) and Assessment

¹If pain score from assessment of response to BPI-SF questionnaire demonstrates an improvement in pain (refer to section 10.4.5) a confirmatory questionnaire at least 2 weeks later will be verbally administered to patients as described for 18-week administration of BPI-SF.

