8.2 INCLUSION CRITERIA

Patients must fulfil all of the following inclusion criteria to be eligible to enrol into the study:

1. Provision of informed consent.
2. ≥ 18 years of age.
3. Histologically confirmed prostate cancer and/or PSA of > 100 ng/mL at original diagnosis
4. Metastatic disease evidenced by either CT/MRI imaging or bone scan.
5. Objective evidence of disease progression as defined by either:
 - i. Radiographic progression of in nodal or visceral metastases and bone disease progression with 2 or more new lesions
 - ii. Rising PSA value ≥ 2 ng/ml in at least 3 measurements, at least 1 week apart, with castrate levels of serum testosterone.
6. Eligible to receive palliative radiation therapy to at least one symptomatic lesion for management of disease.
7. ECOG Performance status 0-2.
8. A minimum life expectancy of 24 weeks.
9. Adequate bone marrow, hepatic and renal function as evidenced by:
 - Absolute neutrophil count (ANC) $> 1.5 \times 10^9$ /L
 - Platelet count $> 100 \times 10^9$ /L
 - Hemoglobin > 9.0 g/dL
 - Serum bilirubin $< 1.5 \times$ ULN
 - AST/ALT (SGOT/SGPT) $< 2.5 \times$ ULN for the reference laboratory or $< 5 \times$ ULN in the presence of liver metastases
 - Serum creatinine $< 1.5 \times$ ULN
10. Ongoing androgen deprivation therapy with luteinizing hormone-releasing hormone (LHRH) agonist or antagonist.
11. At least 4 weeks must have elapsed prior to commencement of NOX66 treatment since prior chemotherapy, investigational drug or biologic therapy and any toxicity associated with these treatments has recovered to \leq NCI-CTCAE (version 4.03) Grade 1.
12. At least 21 days must have elapsed following major surgery and any surgical incision should be completely healed.

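### The age limit for a pre-existing baseline scan runs from screening, not first dose, so tumour change over up to 42 untreated days can be counted as change on treatment

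*Combined protocol and SAP*

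**What the plan says.** Section 10.2.1 lists "Tumour Imaging (CT/MRI) including measures of target lesions- baseline" among the procedures "to be performed at the screening visit to occur within 2 weeks of commencement of NOX66 treatment". Section 10.2 gives the same two-week window: "Screening period: to occur within 2 weeks prior to the scheduled date of treatment commencing".

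Section 10.2.1 then allows an exception. A scan taken in routine practice before consent may be used if the patient agrees to record review, it gives suitable lesion measurements, and "the scans were performed in the 28 days prior to the screening visit (i.e. they can be considered current evidence of tumour size").

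Section 8.4 does not make two weeks a hard stop: "Issues that would cause treatment delays longer than 2 weeks should be discussed with the Sponsor". It does not ask for a new scan in that case.

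The baseline matters in these places:

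- Section 10.4.8 measures partial response as a fall of at least 30% from the baseline sum of longest diameters. It measures progression as a rise of at least 20% from the smallest sum since treatment began, or any new lesion.
- Section 12.1 attributes to NOX66 any response beyond the reduction of under 30% expected from palliative radiation alone.
- Sections 10.2.14 and 13.2 use Week 6 response, with safety and other data, to choose the expansion dose.
- Section 10.1 times progression-free duration from the start of treatment.

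**The concern.** The clause controls how old the scan is at screening. What matters for measuring response is how old it is when treatment starts. Any change in lesion size between the scan and Day 1 enters the on-treatment change, and the amount can differ from patient to patient with scan age.

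The population makes change in the gap plausible. Inclusion criterion 5 in Section 8.2 requires "Objective evidence of disease progression as defined by either" of two routes, radiographic progression or rising PSA. Growth before Day 1 would pull a genuine response towards or below the 30% line. Shrinkage before Day 1 would push in the other direction, and Section 12.1 would credit it to NOX66.

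At stake are the descriptive response results and the Week 6 signals that inform the expansion dose. Escalation cohorts have four patients. If all four were evaluable, reclassifying one would move that cohort's response proportion by 1/4 = 25 percentage points.

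**Working it through.** **Maximum scan age.** The plan states no figure for scan age at first dose, so there is none to reproduce.

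- Scan to screening visit: up to 28 days (10.2.1).
- Screening visit to first NOX66 dose: up to 14 days (10.2, 10.2.1).
- Maximum within the stated windows: 28 + 14 = 42 days, or more if a longer delay is agreed under 8.4.

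**Share of the Week 6 interval that is untreated.** Visit 8 is on Day 43 ± 5 (10.2.4), which is 42 days after Day 1.

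- 42-day-old scan: 42/(42 + 42) = 50%. Over the visit window this runs from 42/89 = 47% to 42/79 = 53%.
- 28-day-old scan: 28/(28 + 42) = 40%.

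**Effect if lesions grow in the gap.** The documents give no growth rate. Assume the sum of diameters grows by r = 10%, 20% or 30% per 84 days, exponentially. For a scan d days before Day 1, the growth factor is f = (1 + r)^(d/84). Then:

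- a true 30% shrinkage from Day 1 is read as 1 − 0.70f;
- the growth from Day 1 that triggers the 20% progression rule is 1.20/f − 1, provided baseline is the reference sum.

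| Scan age at Day 1 | f (r = 10 / 20 / 30%) | True 30% shrinkage reads as | Growth from Day 1 that triggers progression |
|---|---|---|---|
| 42 days | 1.049 / 1.095 / 1.140 | 26.6 / 23.3 / 20.2% | 14.4 / 9.5 / 5.2% |
| 28 days | 1.032 / 1.063 / 1.091 | 27.7 / 25.6 / 23.6% | 16.2 / 12.9 / 10.0% |
| 14 days | 1.016 / 1.031 / 1.045 | 28.9 / 27.8 / 26.9% | 18.1 / 16.4 / 14.9% |

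The 14-day row is the oldest scan possible when imaging is done at a screening visit held within its window.

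**When the progression column applies.** Read literally, Section 10.4.8 takes the smallest sum since treatment began, which leaves out a pre-treatment scan. At Week 6, however, baseline is the only earlier scheduled measurement, so in practice it is the reference there. It stays the reference later only if lesions have not shrunk below baseline. Separately, a lesion that first appears between the scan and Day 1 would be read as new on treatment under either reading.

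**Effect in the other direction.** Inclusion criterion 11 requires at least 4 weeks (28 days) between earlier chemotherapy, investigational or biologic therapy and NOX66. A 42-day-old scan can therefore precede the last dose of that therapy by up to 42 − 28 = 14 days. Late shrinkage from it would count as response after Day 1. With a 28-day limit before Day 1, the scan could no longer precede a last dose given in line with criterion 11.

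**The case against.** The strongest reply is that this is a small matter of degree. The exemption is optional and needs suitable measurements. Size change applies only where there are measurable lesions, and irradiated sclerotic bone lesions are judged locally by the pain questionnaire (10.4.8). The expert committee's overall assessment also uses PSA, ECOG and pain (10.4.9). The primary objective is safety, and the synopsis plans no formal analysis. The fix also moves the example by only about 1 to 3 percentage points: a true 30% shrinkage still reads below 30% in every row of the table. All of this stands and limits the point to a cheap improvement.

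Three stronger readings are tempting, and the documents do not support them:

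- **An old baseline always understates response because every patient is progressing.** Criterion 5 admits patients on rising PSA alone, which does not show that measurable lesions are growing. The 4-week washout also leaves room for bias upward. Where lesions do grow, the error is conservative against the attribution rule in 12.1.
- **Progression is generally called too early.** The sum-based shift holds only while baseline is the reference. Once lesions shrink below baseline on study, scan age no longer affects later sum-based calls.
- **The clause contradicts its own statement that such scans are current.** That statement is tied to the screening visit, and no figure in the documents shows currency to be lost at 42 days.

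What survives the reply is that no section limits scan age at first dose, and that scan age can differ between patients and cohorts with no stated plan to report it.

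**Conclusion.** The point holds as a minor design weakness. The 42-day maximum follows directly from the stated windows. From such a scan, half of the interval to the Day 43 assessment is untreated. That applies to patients who use the exemption and have measurable lesions; the documents do not say how many there will be.

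The size of the effect rests wholly on assumed growth. At 10% to 30% per 12 weeks, a true 30% shrinkage is understated by about 3 to 10 percentage points from a 42-day-old scan, against about 2 to 6 from a 28-day-old one. Slower growth gives less. The direction is conditional: downward if lesions grow in the gap, upward if late shrinkage from earlier therapy falls within it. The effect on progression calls is conditional too, chiefly at Week 6. No alpha or power is involved. What is affected is the descriptive response and progression data and one of the inputs to the expansion-dose decision.

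**What to change.** In Section 10.2.1, change the exemption so that the routine scan must have been performed within 28 days before Day 1 of NOX66. If it is older, use the screening scan that the section already lists. Record the days from baseline scan to Day 1 and list them beside each response, including for patients already enrolled. Section 10.2.7 provides for patients who had completed Visit 10 when the amendment was implemented. For them a changed clause comes too late, and the listing is the only part that helps.

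The cost is one clause and one listed variable. Some patients will lose the exemption and need the scheduled screening scan; the documents do not allow their number to be estimated. The change cuts the maximum age from 42 to 28 days and the untreated share of the Week 6 interval from 50% to 40%. It reduces the bias but does not remove it.
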